5.2.2. Secondary Endpoints(s)

The secondary endpoints include:

- Change of NRS score from baseline at 1 day and 3 months
- Change of ODI from baseline at 1 day, 3-month visit and 6-month visit.
- Change of SF-36 from baseline at 1 day, 3-month visit and 6-month visit
- Change in Vertebral body height restoration at 1 day and 3-month visit and 6 month
- Change in Vertebral body Angles from baseline at 1 day, 3-month visit
- Adverse event through 6-month visit, in particular, the following events will be reported:

- Bone Cement Implantation Syndrome;
- Bone Cement leakage;
- Vertebral body compression fracture;
- Adjacent vertebral body fracture;

6. Study Design

The Xpede Study is a prospective, 1: 1 randomized, single blinded, multi-center human clinical trial designed to confirm the safety and efficacy profile of the Kyphon®Xpede™ Bone Cement for regulatory approval in China. This study will enroll up to 180 subjects in order to demonstrate that the Kyphon®Xpede™ Bone Cement is non-inferior to the Mendec Bone Cement by more than a small pre-specified amount in terms of the primary endpoint. This amount is defined as the non-inferiority margin (section 13 for details). Subjects will be randomly assigned with a 1:1 ratio to the Kyphon®Xpede™ Bone Cement arm or to the Mendec Bone Cement arm and then followed for a duration of 6 months in all sites. All study sites will be in China. All study sites and Investigators are provided under a separate cover.

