9.8. Radiography assessment

Radiological measurements will be made both by the blinded site personnel and by a centralized, independent radiologist (corelab).

A. Vertebral Body Height

Vertebral body height should be assessed at Pre-Operative, 1 days, 3-, 6-month.

Vertebral Body Height in the lateral projection will be measured at each treated vertebra as well as the next adjacent vertebrae (superior and inferior) without fracture and reported in millimeters. Vertebral Body Height is the distance between comparable points on the superior and inferior

endplates of the vertebral body at the posterior (Hp), midline (Hm) and anterior (Ha) locations as shown in Figure 3.

Notes about Adjacent Vertebral Body Height Measurements:

Note 1: The normal estimated pre-fracture height of the treated vertebra will be based on the average of the nearest adjacent non-fractured vertebrae (see Figure 4 below). The reviewer will record the level of the nearest non-fractured level superior to and inferior to the treated level.

Note 2: When L5 is the treated vertebra, the estimated pre-fracture (predicted) height of L5 will be based on L4 or the nearest superior non-fractured level. The height of S1 is not suitable as a predictor of the pre-fracture height of L5.

Note 3: The height of the nearest adjacent, non-fractured, vertebrae may be calculated at a single time point and used for all measurements at other time points. In general, the adjacent level vertebral heights will be obtained at the Pre-Operative time point from standing neutral lateral x-rays.

Note 4: In some cases, the superior or inferior adjacent vertebra may be poorly visualized at the Pre-Operative visit due to inadequate image quality. In this situation, the adjacent vertebra may be excluded from the analysis, or a subsequent visit, e.g. Post-Operative, may be used to obtain a reliable measurement of the adjacent vertebral body height.

- 1) Posterior height (Hp) is obtained by placing a vertical line along the dorsal surface of the vertebral body from the posterior point of the superior vertebral body endplate to the posterior point of the inferior endplate.

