9.10. Assessment of Safety

Timely, accurate, and complete reporting and analysis of safety information is crucial for the protection of subjects, clinicians, and the sponsor. Reporting and analysis of safety data are mandated by regulatory authorities worldwide. Medtronic has established Standard Operating Procedures (SOPs) to ensure compliance with global regulatory safety reporting requirements. Study activities are conducted in accordance with these SOPs.

All adverse events are collected throughout the duration of this study, starting from the time of signing the ICF through study closure. Adverse Events are to be reported upon site awareness using an adverse event CRF, capturing date of the event; date site became aware of the event, diagnosis of the event, actions taken, assessment of seriousness, relatedness and outcome.

Unavoidable Adverse Events (refer to Table 7) need not be reported unless the adverse event worsens or is present outside the stated timeframe.

Adverse Events will be recorded and reported according to local regulatory requirements and are outlined in Table 8. It is the responsibility of the Investigator to abide by the adverse event reporting requirements stipulated by local law and the sites' Ethics Committee.

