4.2. Secondary Objectives and Endpoints

The secondary endpoints include:

- Change of NRS score from baseline at 1 day and 3-month visit
- Change of ODI from baseline at 1 day, 3-month visit and 6-month visit
- Change of SF-36 from baseline at 1 day, 3-month visit and 6-month visit
- Change of Vertebral body height restoration at 1 day and 3-month visit and 6-month visit
- Change of Vertebral body Angles from baseline at 1 day, 3-month visit and 6-month visit
- Adverse events through 6-month visit. In particular, the following events will be reported:
 - Bone Cement Implantation Syndrome;
 - Bone Cement leakage;
 - Vertebral body compression fracture;
 - Adjacent vertebral body fracture;

5. Investigation Plan

The Xpede Study is a prospective, 1: 1 randomized, single blinded, multi-center human clinical trial designed to confirm the safety and efficacy profile of the Kyphon®Xpede™Bone Cement for regulatory approval in China. This study will enroll up to 180 subjects in order to demonstrate that the Kyphon®Xpede™ Bone Cement is non-inferior to the Mendec Bone Cement by more than a small pre-specified amount in terms of the primary endpoint. This amount is defined as the noninferiority margin (see section 13 from Protocol for details). Subjects will be randomly assigned with a 1:1 ratio to the Kyphon®Xpede™ Bone Cement arm or to the Mendec Bone Cement arm and then followed for a duration of 6 months in all sites. All study sites will be in China. Total duration of the study is anticipated to be approximately 12 months (6 months of enrollments and 6 months follow-up after study procedure).

Patients will be randomized 1:1 to either Xpede™ Bone Cement or Mendec bone cement. The sequence of treatments will be randomly permuted in blocks of 2 or 4 patients per block. The

Xpede Clinical Study

Statistical Analysis Plan

Version 1.0

Page 6 of 19

Medtronic

blocked randomization will be centralized and schedules will be created by the study statistician using statistical software. To minimize the selection bias, the randomization procedure for this study will use the site (3 sites), the number of vertebral to be treated (1,2 or 3) and the type of procedure (2 procedure: VP and BKP) as stratification factors, so that there will be a separate permuted block randomization list for each stratum (18). This guarantees treatment balance within strata.

[figure not shown]

Figure 1: Study Flowchart

6. Determination of Sample Size

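### Adjacent vertebral fracture is a named endpoint event, but neither document defines it on X-ray or asks the blinded core lab to look for it

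*Protocol*

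**What the plan says.** Protocol 5.2.2 introduces its safety endpoint with "Adverse event through 6-month visit, in particular, the following events will be reported" and lists four events, one of them "Adjacent vertebral body fracture". SAP 4.2 does the same: "Adverse events through 6-month visit. In particular, the following events will be reported". In both documents the event is classed as an adverse event, not as an imaging result.

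Protocol 9.8 sets the image readings. On timing it says: "Vertebral body height should be assessed at Pre-Operative, 1 days, 3-, 6-month". On which levels, it says height "will be measured at each treated vertebra as well as the next adjacent vertebrae (superior and inferior) without fracture". Note 1 gives the purpose of the neighbours: their average estimates what the treated vertebra measured before it fractured. Note 3 then says the neighbour's height "may be calculated at a single time point and used for all measurements at other time points", and that this is in general the pre-operative visit. Note 4 covers a poor pre-operative view: the neighbour may be left out, or "a subsequent visit, e.g. Post-Operative, may be used to obtain a reliable measurement of the adjacent vertebral body height". The angle is read on fractured vertebral bodies only.

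Protocol 9.9 sends the X-rays to a blinded core lab, whose reading decides the conclusions. It sits under efficacy and names no fracture-detection task. For safety, Protocol 9.10 says: "Adverse Events are to be reported upon site awareness using an adverse event CRF". SAP 7.10 lists adverse event tables by MedDRA class and term, one of them also by relationship to cement, plus listings. SAP 10.3.1 uses the neighbour only at baseline, in the height-restoration calculation.

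**The concern.** A new fracture beside a cemented level is one of the four events the sponsor chose to name, in a trial whose synopsis claims non-inferiority for safety as well as efficacy. Films that could show it are scheduled at 1 day, 3 months and 6 months, and a blinded reader already reviews the X-rays. The plan does not connect the two. No threshold or grade makes a change in a neighbour a fracture, and no reader is told to record one.

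That leaves the site's adverse event report. A fracture that causes no new complaint, or whose pain is put down to the index fracture, may not be reported. The trial is single-blind. Blinding is specified for efficacy evaluation and image measurement, and is not stated for adverse event reporting. The current text also describes no events committee that would review such cases. Equal under-capture would make the absolute difference between cements look smaller than it is. Unequal capture could create or hide a difference.

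**Working it through.** The plan gives no adjacent-fracture rate, so there is no figure of its own to reproduce. The check is a reading of the passages, followed by an illustration.

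**Passages side by side**

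| Question | Adjacent level | Treated level |
|---|---|---|
| Named as an event? | Yes (Protocol 5.2.2, SAP 4.2) | Yes, vertebral body compression fracture (same places) |
| Height read at each follow-up? | The general text of 9.8 says so; Note 3 makes it optional | Yes (9.8 A) |
| Angle read at each follow-up? | Not stated | Yes (9.8 B) |
| Use in SAP 10.3.1 | Baseline reference only | Follow-up height |
| Radiographic definition of a new fracture? | None | None |
| Core lab asked to record a new fracture? | No | No, but it measures height and angle |
| Stated route for counting the event | Adverse event form (9.10) | Adverse event form (9.10) |

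Two things follow. First, the general text of 9.8 and Note 3 pull in different directions on whether neighbours are re-measured, and they need reconciling. Second, the data gap is at the adjacent level. At the treated level the measurements exist and only a threshold is missing.

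**Illustration (rates and capture shares are assumptions)**

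Inputs: n = 90 per arm (Protocol 13.1.2), ignoring loss to follow-up; true 6-month risks of 15% with Xpede and 8% with Mendec; share s of fractures captured, the same in both arms; no false reports.

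Expected reported events = n × risk × s. Reported risk difference = s × (15 − 8) points.

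| s | Xpede events | Mendec events | Difference (points) |
|---|---|---|---|
| 1.00 | 90 × 0.15 = 13.5 | 90 × 0.08 = 7.2 | 7.0 |
| 0.75 | 10.1 | 5.4 | 5.25 |
| 0.50 | 6.8 | 3.6 | 3.5 |
| 0.25 | 3.4 | 1.8 | 1.75 |

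The risk ratio stays at 15/8 = 1.875 throughout. Equal under-capture shrinks the absolute difference and the event count, not the ratio.

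With assumed risks of 10% and 20%, the power of a two-sided 0.05 comparison with 90 per arm is 0.47 with full capture (9 against 18 events) and 0.25 with half captured (4.5 against 9).

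Unequal capture behaves differently. With the same true risk of 10% in both arms and capture of 75% in one and 50% in the other, the reported difference is 10 × (0.75 − 0.50) = 2.5 points, with no true difference. With 75% against 25% it is 5 points.

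**The case against.** The strongest reply has five parts.

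- **Note 3 is not the culprit.** It is permissive, and a fixed reference is sound for estimating pre-fracture height. A reader might infer that it forbids re-measuring neighbours or noting a fracture; it does neither. This stands. The gap is the missing definition and the unassigned task, with Note 3 making re-measurement optional.
- **Sites see the films.** Site personnel measure the same X-rays, adverse events are collected at the same visits, and the adverse event definition does not require symptoms. So the documents do not support saying that silent fractures will go uncounted, only that nothing ensures they are counted. Nor do they say that the person reporting is unblinded; they are silent.
- **Treated levels are covered.** It would be tempting to say that collapse there depends equally on adverse event reports. It does not: height and angle are read centrally at each visit.
- **Note 4 is largely contained.** A reader might infer that a collapsed neighbour would become the reference. Section 9.8 restricts references to unfractured vertebrae, the example it gives is the post-operative visit, and SAP 10.3.1 takes the neighbour at baseline. What remains is a point of wording.
- **Other papers may fill the gap.** The mock tables are in a separate file, and no core-lab reading manual was available. Either might cover this, in which case a cross-reference would be enough.

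It is also true that complete reading would seldom settle the comparison: at 15% against 8% with 90 per arm, power is only about 31%. The case for the change is an unbiased, complete count, not a decisive test.

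**Conclusion.** The point holds as a gap in definition and assignment. An event both documents name has no radiographic definition, no assigned blinded reader, and one stated capture route whose blinding is not specified. It concerns a secondary safety event and touches neither primary endpoint. Treated-level collapse is affected less.

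The size cannot be established from the documents. The figures above show only the mechanism: under equal capture the reported difference is the true difference multiplied by the share captured, and under unequal capture a difference can appear where there is none. The conclusion rests on the protocol and SAP being the full instruction to readers and sites on this event. The change is worth making because the films and the blinded reader are already in place.

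**What to change.** - **Protocol 9.8, Note 3.** Keep the pre-operative adjacent height as the fixed reference. Add that the core-lab reader also assesses the superior and inferior adjacent vertebrae on each 1-day, 3-month and 6-month lateral film, and records new adjacent fracture yes or no against the pre-operative film. Fix the height-loss threshold in writing before any film is read. This also reconciles Note 3 with the four-visit schedule. A threshold set the same way would serve for treated-level collapse, using measurements already taken.
- **SAP.** Add one table of core-lab adjacent-fracture rates by arm beside the rates reported as adverse events, with a stated rule for core-lab fractures that have no adverse event record.
- **Note 4 (minor).** State that a substitute reference film must show the neighbour unfractured, preferably the 1-day film.
- **Film wording (minor).** The schedule in Protocol 9.1 lists AP and lateral views, while 9.4 and 9.7 mention only A/P. Align them, since this reading needs the lateral view.

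Cost: a few more measurements per film by the existing reader, short text changes and one table. No new visit, film or reader is needed. The downside is slightly more reading time and more fractures to report in both arms, some of them asymptomatic.

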9.9. Assessment of Efficacy

Efficacy will be evaluated by the blinded investigator or designated blinded site personnel status of primary endpoint and secondary endpoints related with efficacy.

X-ray images will be reviewed by an independent radiological reviewer (Corelab) who will be blinded to the subjects' treatment groups for each analysis.

Adjudications provided both by the site blinded personnel and by the Corelab will be analyzed separately and reported in the Clinical Study Report (CSR). Final conclusion will be made according to Corelab adjudication.

9.10. Assessment of Safety

Timely, accurate, and complete reporting and analysis of safety information is crucial for the protection of subjects, clinicians, and the sponsor. Reporting and analysis of safety data are mandated by regulatory authorities worldwide. Medtronic has established Standard Operating Procedures (SOPs) to ensure compliance with global regulatory safety reporting requirements. Study activities are conducted in accordance with these SOPs.

All adverse events are collected throughout the duration of this study, starting from the time of signing the ICF through study closure. Adverse Events are to be reported upon site awareness using an adverse event CRF, capturing date of the event; date site became aware of the event, diagnosis of the event, actions taken, assessment of seriousness, relatedness and outcome.

Unavoidable Adverse Events (refer to Table 7) need not be reported unless the adverse event worsens or is present outside the stated timeframe.

Adverse Events will be recorded and reported according to local regulatory requirements and are outlined in Table 8. It is the responsibility of the Investigator to abide by the adverse event reporting requirements stipulated by local law and the sites' Ethics Committee.

9.11. Recording Data

Clinical data will be collected at baseline, operative day, 1 day post-operative, 3-month and 6-month post-operative visits. Data will be collected using electronic case report forms (eCRFs) using an electronic data management system for clinical studies. Data will be stored in a secure, password-protected database, which will be backed up nightly. Data will be reviewed using programmed and manual data checks. Data queries will be made available to study sites for resolution. At the end of the study, the data will be frozen and retained indefinitely by Medtronic.

Medtronic will oversee all data management functions and provide support if necessary. Leading site will be accountable for data management and analysis about the study data in a centralized manner according to local regulations.

9.12. Deviation Handling

A deviation is defined as an event within a study that did not occur according to the CIP or the Clinical Trial Agreement. Prior approval by Medtronic is expected in situations where the investigator anticipates, contemplates, or makes a conscious decision to deviate. Prior approval is not required when a deviation is necessary to protect the life or physical well-being of a subject in an emergency or in unforeseen situations beyond the investigator's control (e.g., subject failure to attend scheduled follow-up visits, inadvertent loss of data due to computer malfunction or inability to perform required procedures due to subject illness).

All study deviations must be reported on the Case Report Form regardless of whether medically justifiable, pre-approved by Medtronic, an inadvertent occurrence, or taken to protect the subject in an emergency. The description of the deviation and justification must be documented.

Once a deviation has been identified it should be reported to Medtronic as soon as possible. Deviations may be identified through numerous sources, including but not limited to: telephone conversations, site monitoring, subject record, or data review.

It is the site's responsibility to report deviations in compliance with their EC/IRB policies and/or local laws.

For medically justifiable conditions which preempt a subject's ability to complete a study-required procedure, it may be permitted to complete only one deviation which will apply to all visits going forward. This may also apply for other unforeseen situations (e.g., the subject permanently refuses to complete a study required procedure and the data will not contribute to the primary end point analysis). However, prior approval from Medtronic is required for such situations.

In the occurrence of a corrupted device interrogation file, Medtronic may request a deviation to document that a readable interrogation file is unavailable. Deviations for missing device interrogation file(s) and missing or incomplete electrical testing at the same visit may be reported on one deviation CRF.

In the event the deviation involves a failure to obtain a subject's informed consent, or is made to protect the life or physical well-being of a subject in an emergency, the deviation must be reported to the IRB and Medtronic within five (5) working days. Reporting of all other study deviations should comply with IRB policies and/or local laws and must be reported to Medtronic as soon as possible upon the site becoming aware of the deviation. Reporting of deviations must comply with EC policies, local laws, and/or regulatory requirements.

Medtronic is responsible for analyzing deviations, assessing their significance, and identifying any additional corrective and/or preventive actions (e.g., amend the CIP, conduct additional training, and terminate the investigation). Repetitive or serious investigator compliance issues may represent a

Medtronic Confidential

need to initiate a corrective action plan with the investigator and site, and in some cases, necessitate suspending enrollment until the problem is resolved or ultimately terminating the investigator's participation in the study.

9.13. Subject Withdrawal or Discontinuation

Every attempt should be made to follow all treated subjects through study closure.

Upon exiting from the study, no further study data will be collected or study visits will occur for the subject. No study specific medical care will be provided for subjects after the study has been completed and subject will be treated according to the standard routine practice after the study period.

All data available through the time of the subject's exit will be used for analysis. In the event of study exit, the investigator should discuss with the subject the plans for future care and treatment. The investigator should explain that the subject will continue to receive standard medical care. Alternative treatment, such as medication options, or follow-up through standard of care procedures instead of study procedures, and medical consequences should also be discussed. The investigator must notify the subject of any significant new findings that may become available during the course of the study, which are pertinent to the safety and well-being of the subject.

Exit

Subjects may be exited from the study for any of the following situations:

- Subject does not meet inclusion/exclusion criteria and has not been treated
- No BKP or VP attempted
- Procedure attempted but no bone cement was injected
- Subject chooses to withdraw from the study
- Investigator deems withdrawal necessary (medically justified or inclusion/exclusion criteria not met, failure of subject to maintain adequate study compliance)

In the event that a subject is exited from the study prior to study closure, all efforts should be made to continue following the subject until all unresolved procedure or product related adverse events are resolved or they are ongoing and no further actions will be taken.

Lost to Follow-up

In the case that the subject is determined to be lost to follow-up, details of a minimum of three attempts and the method of attempt (e.g., one letter and two phone records or two letters and one phone record) to contact the subject must be recorded. In addition, the requirements set by the governing EC/IRB for subjects lost to follow-up must be followed.

10. Risks and Benefits

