13.4. Analysis of Clinical Data

Patient demographics and baseline characteristics will be presented using appropriate summary statistics. This includes mean and standard deviation, minimum, maximum and median with the interquartile range [IQR] for continuous variables, and counts and percentages for categorical variables. Summary statistics will be reported with maximum 2 decimals, as appropriate. The SAS software (SAS Institute Inc., Cary, NC, USA) or any other validated Statistical Software will be used to perform statistical analyses. The test for a treatment effect corresponds to showing that the upper bound of the two-sided 95% confidence interval (equivalent to the lower bound of a one-sided 97.5% confidence interval) for $\mu_E(t) - \mu_C(t) < \text{margin}$. Graphical representations will be used as deemed appropriate. No adjustments for multiple comparisons or multiple look at data will be performed. Outliers and influential observations will be identified via graphical plots and according to study team decision and the analysis could be repeated excluding potential outliers. In case of missing data, the imputation of missing data will be performed using the most appropriate method depending on the pattern of missing in the data and the type of the imputed variable. After the imputation of the missing values the models will be rerun.

The data will be analyzed according to the intention-to-treat principle and a Full Analysis Set (FAS) will be used for primary final analysis. The FAS is the patient set containing all the patients included in the study that have signed the study Informed Consent and have received the study treatment. A secondary analysis could be performed on a Per Protocol Set (PPS). The PPS patients set containing all the patients that meet the inclusion/exclusion criteria with no other major protocol deviation that

could impact the clinic outcomes and have the 6 months follow-up visits completed. Any patient who does not satisfy the inclusion/exclusion criteria or receives the wrong treatment will be eliminated from the per-protocol population. Details of endpoints analyses and additional analysis will be described in the Statistical Analysis Plan.

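### Protocol 9.13 lets the investigator exit an already treated subject for failed eligibility or poor compliance and then ends data collection, so the primary analysis can lose 6-month outcomes for reasons linked to interim results

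*Protocol*

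**What the plan says.** Protocol 9.13 opens with a general aim: "Every attempt should be made to follow all treated subjects through study closure". Its exit list then deals with ineligibility twice. The first reason is limited: "Subject does not meet inclusion/exclusion criteria and has not been treated". The last is not: "Investigator deems withdrawal necessary (medically justified or inclusion/exclusion criteria not met, failure of subject to maintain adequate study compliance".

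On what follows exit, the section says: "Upon exiting from the study, no further study data will be collected or study visits will occur for the subject". It keeps what was already recorded ("All data available through the time of the subject's exit will be used for analysis") and continues one kind of follow-up: "all efforts should be made to continue following the subject until all unresolved procedure or product related adverse events are resolved".

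On the analysis side, Protocol 13.4 states: "The data will be analyzed according to the intention-to-treat principle and a Full Analysis Set (FAS) will be used for primary final analysis". The FAS consists of patients who "have signed the study Informed Consent and have received the study treatment". SAP 7.1.3 adds enrolment and randomization. Neither definition removes a subject because of exit. SAP 7.4 says that the outcome variable is not imputed, and Protocol 13.4 analyses NRS with one measure per patient.

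**The concern.** Subjects who are ineligible and untreated are already covered by the first exit reason. The only thing the ineligibility ground in the last reason adds is the power to exit subjects who have received cement. The treatment is a single procedure, so ineligibility found later, or poor compliance with visits, is no reason to stop measuring the 6-month outcome.

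An exit can follow the day-1 and 3-month NRS and X-rays (Protocol 9.1). Several exclusions rest on judgement: pain from other spine disease (exclusion 2), contraindications by the investigator's decision (5) and the investigator's opinion on participation (11). Exclusion 2 is easily reconsidered when pain persists. Blinding is stated for the efficacy assessors and the core laboratory (Protocol 9.8 and 9.9), but 9.13 does not require the person who decides an exit to be blinded.

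If poor responders were exited more often from the Xpede arm, the observed 6-month NRS difference would shift toward non-inferiority. The Per Protocol Set (PPS) would not reveal this. It requires a completed 6-month visit, so the same patients are missing there too. The SAP specifies no sensitivity analysis for missing 6-month outcomes.

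**Working it through.** **What happens to a treated subject exited before month 6**

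1. Exit is permitted by the last reason in 9.13.
2. Collection stops, except for unresolved procedure- or product-related adverse events.
3. The subject remains in the FAS, because membership depends on treatment.
4. There is no 6-month NRS or angle. Protocol 13.4 leaves imputation open in general terms, but SAP 7.4 excludes it for the outcome.
5. With one NRS measure per patient, the subject contributes nothing to the 6-month comparison.

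**The plan's own figure**

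Inputs from Protocol 13.1.2: margin 1.5, SD 3.27, one-sided alpha 0.025, power 80%. The noncentral t calculation gives power 0.797 at 75 per arm and 0.802 at 76, so 152 in total. Allowing for 15% loss, 152 / 0.85 = 178.8, or 179, which the plan rounds to 180. The stated size is reproduced.

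**Illustration of selective exit**

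These assumptions are not in the documents: the true difference equals the margin of 1.5, the analysis is complete-case, *n* = 76 evaluable per arm before exits, *k* exits occur in the Xpede arm only, and those exited average *d* points worse at 6 months than their arm.

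- Shift in the Xpede mean = *k·d* / (*n* − *k*)
- SE = 3.27 × √(1/(*n* − *k*) + 1/*n*)
- One-sided error = Φ(shift / SE − 1.96)

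| *k* | *d* | Shift | SE | Error |
|---|---|---|---|---|
| 0 | – | 0 | – | 2.5% |
| 5 | 2 | 10/71 = 0.141 | 0.540 | 4.5% |
| 5 | 3 | 15/71 = 0.211 | 0.540 | 5.8% |
| 8 | 2 | 16/68 = 0.235 | 0.546 | 6.3% |
| 8 | 3 | 24/68 = 0.353 | 0.546 | 9.5% |

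**A second mechanism, by simulation**

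Here 90 per arm are randomized, the Xpede patients with the worst 3-month NRS are exited, the correlation between 3 and 6 months is 0.3 to 0.7, and the test is a complete-case t-test at the margin.

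| Exited of 90 | Bias (points) | One-sided error |
|---|---|---|
| 2 | −0.05 to −0.12 | 3.1–4.6% |
| 4 | −0.10 to −0.22 | 4.0–6.9% |
| 9 | −0.19 to −0.44 | 5.6–15.1% |

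The two calculations agree in direction and in order of magnitude.

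**The case against.** Several stronger readings are tempting, and the documents do not support them.

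- **That the primary analysis set loses the patient.** It does not. FAS membership rests on treatment, and data up to exit are used. One could argue that the SAP's FAS requires enrolment and that Protocol 8.2 defines enrolment as meeting all criteria. But SAP 7.7 ties enrolment to eligibility confirmed at screening, which weakens that argument.
- **That exit follows sight of the primary outcome.** A recorded 6-month value is kept. Only interim results can precede a harmful exit.
- **That nothing can recover the loss.** SAP 7.2 names MMRM for the primary endpoint. If that applies across NRS visits, day-1 and 3-month scores would contribute, and exit driven by a recorded 3-month score is the case such a model handles. It would not handle exit based on unrecorded impressions. It also sits badly with the single measure per patient in Protocol 13.4, which needs reconciling.
- **That the treating investigator knows the cement.** This is an inference from the single-blind design and is not stated.
- **That both co-primaries are biased.** The mechanism concerns persistent pain. No link to the angle was calculated.

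The other side has further fair points. Exit is permissive and must be deemed necessary. Reasons for premature termination are collected (Protocol 9.1), disposition is reported by group with reasons where known (SAP 7.1.1), and a missing 6-month assessment is a major deviation (SAP 7.1.2), so a marked imbalance would be visible. The illustration is one-sided: with equal *k* and *d* in both arms, the shifts cancel. The exits also come on top of the 15% loss already allowed for.

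The case *d* = 3 is severe. At the margin the Xpede mean is 3.5 + 1.5 = 5.0, so exited patients would average 8.0 at month 6. If exit is decided on the interim score alone, with equal means and SDs at both visits, their interim average would be 5 + 3/0.5 = 11 at a correlation of 0.5, which is off the 0–10 scale, and 5 + 3/0.7 = 9.3 at 0.7.

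These points limit the size of the problem. They do not close the wording gap: visibility after the fact does not restore an outcome that was never measured.

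**Conclusion.** The point holds in a limited form. Section 9.13 permits investigator-decided exit of treated subjects for ineligibility or non-compliance and then ends collection of the 6-month outcomes. That conflicts with the section's opening aim and with an intention-to-treat primary analysis, and the outcome is not imputed.

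The potential inflation of the NRS error, to about 4.5–5.8% with five exits and 6.3–9.5% with eight, depends wholly on assumed Xpede-only selective exits and a complete-case analysis. It is not a forecast. Study success also requires the angle endpoint, so these figures are an upper bound on the rate of false study success in the same scenario. The text gap is certain, the size of its effect is not, and closing it is a cheap improvement.

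**What to change.** In Protocol 9.13:

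1. Reconcile the two eligibility reasons so that exit for ineligibility applies only to untreated subjects.
2. Remove non-compliance as a reason to end data collection in treated subjects.
3. Amend the sentence that stops data collection at exit. Any treated subject, including one withdrawn by the investigator for medical reasons, is still asked for the 6-month NRS and X-ray unless consent is withdrawn, the subject dies or is lost to follow-up. Medically justified withdrawal itself stays as it is; only the measurement continues.

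In Protocol 13.4 and SAP 7.1.3, state that ineligibility found after treatment removes a subject from the PPS only, never from the FAS. It would also help to report exits by arm, reason and timing, and to add a sensitivity analysis for missing 6-month values.

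The cost is a few lines of text and a few extra follow-up visits. The sample size does not change.
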